9.5.1 Sensitivity Analysis of the Primary Endpoint

Sensitivity analyses will not be performed for the purposes of the abbreviated CSR.

9.6 Analysis of Secondary Efficacy Endpoints

The secondary efficacy variables of HiSCR50, HiSCR90 and HiSCR100 at Week 12 will be analyzed using the same approach as the primary efficacy analysis.

9.6.1 Subjects Experiencing HS Flares through Week 12

The statistical null and alternative hypotheses to be used to assess HS Flare are:

$$H_0: \pi_{ABY} - \pi_{PBO} = 0$$

$$H_A: \pi_{ABY} - \pi_{PBO} \neq 0$$

where π_{ABY} and π_{PBO} are the proportion of subjects experiencing HS flares at any time from first dose of study treatment through Week 12 among subjects randomly assigned to receive izokibep and placebo, respectively.

Subjects who received an oral antibiotic that could impact HS at any point before the Week 12 assessment or subjects who discontinue treatment due to AE or lack of efficacy will be included in the analysis with NRI (did experience HS flare). All subjects with missing abscess, inflammatory nodule, or draining tunnel counts will be included in the multiple imputation. The multiple imputation process will be the same as described for HiSCR75, except that draining fistula counts do not play a role in flare and will therefore not be imputed when missing.

Subjects with missing AN counts at any scheduled visit (week 4, week 8, and/or week 12) will have their abscess and inflammatory nodules counts imputed (separately) for each visit with missing data. The imputed counts will be summed and compared to criteria for flare. If the observed or imputed value at any visit meets the definition of flare, the subject will be counted as having a flare; otherwise, the subject will be counted as not having a flare. A total of 100 imputations will be imputed to form the complete data set with a pre-specified seed (3617627) to ensure reproducibility. These multiple imputed data sets will then be analyzed by using the same method for the primary analysis for complete data. The final inference on treatment difference is conducted from the multiple datasets using Rubin's combining rules. Other imputation, fully conditional specification method may be implemented if the multiple imputation model does not converge. Troubleshooting (removing predictor variables or increasing the number of iterations) will be done in the same manner as for the primary endpoint.

The number and proportion of subjects for subjects who experience a HS flare through Week 12 in each treatment group will be reported analogous as the primary endpoint.

9.6.1.1 *Sensitivity Analysis of Subjects Experiencing HS Flares through Week 12*

Sensitivity analyses will not be done for the purposes of the abbreviated CSR.

9.6.2 *Change from Baseline in DLQI at Week 12*

DLQI mean values, mean changes and associated descriptive statistics along with 95% CI (for change from baseline) through Week 12 for each treatment group will be provided.

Treatment policy estimand strategy will be used, in general, with all subjects included in the analysis regardless of treatment discontinuation, concomitant medication/rescue medication, protocol deviations, or other actions.

DLQI change from baseline will be analyzed using a mixed model repeated measure (MMRM). The model for the comparison will include treatment, baseline DLQI, stratification factors, visit week, and treatment by visit week interaction as covariates. LS (least square) mean changes and associated SEs with associated 95% CI and p-values will be presented. Model will include all data up to Week 12. An unstructured (UN) covariance matrix will be used. Other variance-covariance matrices, such as autoregressive (AR), and compound-symmetric (CS) will be considered and specified in the footnote if the model does not converge. Sample code is as follows:

```
proc mixed ;
  class week stratum1 stratum2 subjectid treatment(ref = "placebo")
  model change_dlqi = base_dlqi stratum1 stratum2 week treatment treatment*week
  repeated week / subject = subjectd (treatment) TYPE = UN;
  lsmeans treatment*week /slice = week cl;
  slice treatment*week/ sliceby = week pdiff cl;
run;
```

9.6.3 Baseline Hurley Stage II Subjects who Achieve AN count of 0, 1, or 2 at Week 12

The secondary endpoints of percentage of subjects with baseline actual Hurley Stage II who achieved AN count of 0, 1, or 2 at Week 12 will be analyzed analogously to the primary endpoint. The statistical null and alternative hypotheses to be used to assess these objectives are:

$$H_0: \pi_{ABY} - \pi_{PBO} = 0$$

$$H_A: \pi_{ABY} - \pi_{PBO} \neq 0$$

where π_{ABY} and π_{PBO} are the proportion achieving AN count of 0, 1, or 2 at Week 12 among subjects randomly assigned to receive izokibep and placebo, respectively.

Subjects who have missing data at Week 12 due to discontinuation of treatment due to adverse event or lack of efficacy or who received an oral antibiotic that could impact HS will be included in the analysis with NRI (did not achieve AN count of 0, 1, or 2). Other missing data will be handled using multiple imputation analogously to the primary endpoint. Only subjects with Hurley Stage II at baseline will be included in the hypothesis test for AN count, while other subjects will be summarized, and a p-value reported for descriptive use only.

Hurley stage collected in the eCRF ('worst case' Hurley stage from the baseline Lesion Counts eCRF page) will be used.

Methodology will be identical to that used for the primary endpoint with the exception of stratification factors. For the secondary endpoint, achieve AN count of 0, 1, or 2 at Week 12, which uses only subjects with Hurley Stage II at baseline, the stratification factor of baseline Hurley Stage will be omitted from the analysis. For the analysis using all subjects, the stratification factor of baseline Hurley Stage will be used, as in the primary endpoint analysis.

9.6.4 NRS of Skin Pain at Week 12

The secondary endpoint of percentage of subjects achieving at least 3 points reduction from baseline in NRS in Patient Global Assessment of Skin Pain at its worst at Week 12 among participants with baseline NRS ≥ 3 will be analyzed analogously to the primary endpoint.

The number and proportion of subjects achieving at least 3 points reduction from baseline in NRS in Patient Global Assessment of Skin Pain at its worst at Week 12 among participants with baseline NRS ≥ 4 in each treatment group will be reported.

Subjects who have missing data at Week 12 due to discontinuation of treatment due to adverse event or lack of efficacy will be included in the analysis with NRI (did not achieve least 3 points reduction from baseline in NRS in Patient Global Assessment of Skin Pain at its worst). If a subject received certain prohibited analgesic therapy within 28 days of the visit (including the day of the visit) for HS indication, then the visit within the 28 days of the start date of the prohibited analgesic will be imputed as NRI.

If a subject received certain prohibited analgesic therapy within 28 days of the visit (including the day of the visit) for non-HS indication, the subject will have the pain scores after such use of prohibited pain medication omitted from the dataset due to the ICE and replaced via multiple imputation in a model analogous to the one used for the primary analysis. This process will only be done for the visit(s) within

28 days of the start date of the prohibited analgesic therapy for non-HS indication. For the multiple imputation, the model used will be analogous to the one for the primary endpoint, however the baseline NRS (at its worst) score will be added as a baseline covariate. In addition, the imputation will be done for the average NRS value for the visit.

Other missing data will be handled using multiple imputation analogously to the primary endpoint (including baseline NRS [at its worst] score as a covariate in the model).

Allowable and prohibited analgesics are pre-specified in sections 6.8.2.3 (Analgesic Therapy) and 6.8.3 (Prohibited Medications) of the protocol. A final list of all subjects who took prohibited analgesic therapy which results in NRI or data omission and subsequent multiple imputation will be created after the data is final and before unblinding and will include justification for choosing the subjects based on specific analgesic, timing relative to the visit, and other factors considered.

Since the NRS in Patient Global Assessment of Skin Pain is collected as a daily diary, the score used for analysis will be the average of the scores recorded 6 days prior to and the day of the visit (7 days total for the average). If scores are recorded on fewer than 3 of these 7 days, the pain score will be treated as missing; otherwise, the mean of the observed values (up to 7) will be used. The same approach to calculating the average value will be used for any visit occurring through Week 16 visit, including End of Treatment visits windowed to a visit on or before Week 16.

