- Treatment: izokibep versus placebo
- Population of interest: subjects with HS who meet all inclusion/exclusion criteria
- Variable of interest: change in HS flares after 12 weeks of treatment
- Summary measure: response rate, improvement in HS flare occurrence (Yes/No)

- ICE handling: treatment policy strategy, with all subjects included in the analysis regardless of treatment discontinuation, concomitant medication/rescue medication, protocol deviations, or other actions. All subjects with missing abscess, inflammatory nodule, and draining tunnel counts will be included using multiple imputation, analogously to the analysis of the primary endpoint. Subjects who receive antibiotic therapy that could affect HS will be included in the analysis by assigning non-response at subsequent timepoints. Multiple imputation and non-response imputation will be used to handle certain other types of missing data, analogously to the primary endpoint.

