Subjects who receive antibiotic therapy that could affect HS will be included in the primary analysis by assigning non-response at subsequent timepoints. A list of all oral antibiotic therapy that results in such imputation will be finalized after review of all oral antibiotic therapy received by any subject and before unblinding of the study, and will include tetracycline, clindamycin, and possibly other products. Similarly, subjects who discontinue treatment due to an AE or lack of efficacy, and subsequently have missing efficacy responses, will be included by imputing non-response. Other subjects with missing data will have efficacy data imputed using multiple imputation. The imputation model will use data from placebo subjects and include baseline characteristics and demographics, factors used for stratification of randomization, and observed efficacy at earlier timepoints, and will be fully defined before unblinding. The model will impute components of the primary endpoint (abscess count, inflammatory nodule count, and draining tunnel count) separately. The imputation model will be run multiple times (eg, 100 times) and the results analyzed for each run using the primary analysis methodology. Results from all runs will be combined using Rubin's rule, resulting in a single point estimate, a single CI, and a single p-value. The number of subjects imputed with non-response imputation and the number imputed with multiple imputation will be tabulated with reasons for imputation at Week 12.

Supportive analyses using other assumptions about ICEs will also be reported. These will be defined before the database is locked and treatment assignments are unblinded.

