6.7.1 Estimand for Primary Endpoint

The primary estimand is defined through the 5 attributes described in the following sections.

6.7.1.1 *Treatment Condition of Interest*

The primary treatment condition of interest is izokibep versus placebo.

6.7.1.2 *Population of Interest*

The population of subjects is those who are 18 years and older with moderate to severe HS (HS lesions present in ≥ 2 distinct anatomic areas, 1 of which must be Hurley Stage II or Hurley Stage III, and a total AN count of ≥ 5) who meet all inclusion criteria and exclusion criteria.

6.7.1.3 *Variable of Interest*

The endpoint for each subject to address the clinical question is achievement of HiSCR75 after 12 weeks of treatment.

6.7.1.4 *Intercurrent Event (ICE)*

The treatment policy strategy approach will be used in general. Thus, all subjects will be included using observed data at Week 12 regardless of treatment discontinuation, concomitant medication/rescue medication, protocol deviations, or other actions.

Subjects who receive antibiotic therapy that could affect HS will be included in the primary analysis by assigning non-response at subsequent timepoints. A list of all oral antibiotic therapy that results in such imputation will be finalized after review of all oral antibiotic therapy received by any subject and before unblinding of the study, and will include tetracycline, clindamycin, and possibly other products. Similarly, subjects who discontinue treatment due to an AE or lack of efficacy, and subsequently have missing efficacy responses, will be included by imputing non-response.

Multiple Imputation will be used to handle other types of missing data as described in [Section 9.5](#).

6.7.1.5 *Population Level Summary*

The population level summary is the response rate, or proportion of subjects who meet HiSCR75 after 12 weeks of treatment.

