	Intercurrent Event	Treatment policy strategy, in general, with all subjects included in the analysis regardless of treatment discontinuation, concomitant medication/rescue medication, protocol deviations, or other actions. Subjects who receive antibiotic therapy that could affect HS will be included in the primary analysis by assigning non-response at subsequent timepoints. Multiple imputation and non-response imputation will be used to handle certain other types of missing data, analogously to the primary endpoint.
	Population Level Summary	Response Rate of HiSCR50 at Week 12 (Yes/No)
HS Flares Through Week 12	Treatment Condition of Interest	izokibep versus placebo
	Population of Interest	Subjects with HS who meet all inclusion/exclusion criteria
	Variable of Interest	Change in HS flares after 12 weeks of treatment
	Intercurrent Event	Treatment policy strategy, with all subjects included in the analysis regardless of treatment discontinuation, concomitant medication/rescue medication, protocol deviations, or other actions. All subjects with missing abscess, inflammatory nodule, and draining tunnel counts will be

		included using multiple imputation, analogously to the analysis of the primary endpoint. Multiple Imputation described in Section 9.6.1 . Subjects who receive antibiotic therapy that could affect HS will be included in the primary analysis by assigning non-response at subsequent timepoints. Multiple imputation and non-response imputation will be used to handle certain other types of missing data, analogously to the primary endpoint.
	Population Level Summary	Improvement in HS flare occurrence (Yes/No)
Change in DLQI from baseline to Week 12	Treatment Condition of Interest	izokibep versus placebo
	Population of Interest	Subjects with HS who meet all inclusion/exclusion criteria
	Variable of Interest	DLQI after 12 weeks of treatment
	Intercurrent Event	Treatment policy strategy, in general, with all subjects included in the analysis regardless of treatment discontinuation, concomitant medication/rescue medication, protocol deviations, or other actions
	Population Level Summary	Mean change from baseline in DLQI
AN count of 0, 1, or 2 at Week 12	Treatment Condition of Interest	izokibep versus placebo
	Population of Interest	Subjects with HS who meet all inclusion/exclusion criteria and with baseline Hurley Stage II
	Variable of Interest	Percentage of subjects achieving AN count of 0, 1, or 2 at Week 12

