9.5 Analysis of Primary Efficacy Endpoint

The primary efficacy variable is defined as HiSCR75 at Week 12.

The statistical null and alternative hypotheses to be used to assess the primary objective are:

$$H_0: \pi_{ABY} - \pi_{PBO} = 0$$

$$H_A: \pi_{ABY} - \pi_{PBO} \neq 0$$

where π_{ABY} and π_{PBO} are the proportion of subjects achieving HiSCR75 at Week 12 among subjects randomly assigned to receive izokibep and placebo, respectively.

The treatment policy strategy approach for the estimand will be used in general, so subjects will be included using observed data at Week 12 regardless of treatment compliance, use of rescue medications or procedures except as noted below, or any other protocol deviations.

Subjects who receive antibiotic therapy that could affect HS will be included in the primary analysis by imputing as non-responders (non-response imputation or NRI) at subsequent timepoints. A list of all oral antibiotic therapy that results in such imputation will be finalized after review of all oral antibiotic therapy received by any subject and before unblinding of the study, and will include tetracycline, clindamycin, and possibly other products. Similarly, subjects with missing HiSCR75 assessments at Week 12 due to discontinuing treatment due to an AE or lack of efficacy will also be imputed as NRI. These subjects will be identified by meeting any of the following criteria:

- Subject has adverse event with action taken = “Drug Withdrawn” and corresponding AE start date is before study day 84 and last dose of study drug is taken before study day 84 or
- Subject has last dose of study drug taken before study day 84 and reason for discontinuation of treatment is any of the following:
 - Adverse event
 - Death
 - Lack of efficacy
 - Disease progression

Other subjects with missing data will have efficacy data imputed using multiple imputation, as follows:

Multiple imputation will be implemented to replace missing endpoint data using multiple draws from a posterior predictive distribution estimated from the placebo group only. First, a monotone missingness pattern will be enforced using Markov Chain Monte Carlo (MCMC). The MCMC process will use predictor variables of:

- baseline abscess count (continuous)
- baseline inflammatory nodule count (continuous)
- baseline draining fistula count (continuous)
- age (continuous)
- baseline BMI (continuous)

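### SAP 9.6.1 counts every subject who stops treatment for an AE or lack of efficacy as a flare, even with observed flare-free counts, which contradicts the flare estimand

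*SAP*

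**What the plan says.** SAP 9.6.1 sets flare to yes for two groups in a single sentence. The first is subjects who took an HS-relevant oral antibiotic, and this clause is limited to use before the Week 12 assessment. The second reads: "subjects who discontinue treatment due to AE or lack of efficacy will be included in the analysis with NRI (did experience HS flare"). That clause has no missing-data condition and no time limit of its own. The next paragraph of 9.6.1 decides flare status from observed or imputed counts at each visit and counts everyone else as flare-free.

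The parallel rules are narrower:

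- **SAP 9.5 (primary):** NRI applies to "subjects with missing HiSCR75 assessments at Week 12 due to discontinuing treatment due to an AE or lack of efficacy". The subjects are identified by criteria such as "Subject has last dose of study drug taken before study day 84 and reason for discontinuation of treatment is any of the following"; the reasons listed are adverse event, death, lack of efficacy and disease progression.
- **SAP 6.7.1.4:** those who stop for these reasons and "subsequently have missing efficacy responses, will be included by imputing non-response".
- **Protocol 9.3.2:** "subjects who discontinue treatment due to an AE or lack of efficacy, and subsequently have missing efficacy responses, will be included by imputing non-response".
- **SAP 9.6.3 and 9.6.4 (AN count, pain):** "Subjects who have missing data at Week 12 due to discontinuation of treatment due to adverse event or lack of efficacy".

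The flare estimand in SAP Table 5 is "Treatment policy strategy, with all subjects included in the analysis regardless of treatment discontinuation, concomitant medication/rescue medication, protocol deviations, or other actions", and Protocol Section 3 agrees. Both then apply to flare the sentence used for the other responder endpoints: "Multiple imputation and non-response imputation will be used to handle certain other types of missing data, analogously to the primary endpoint". SAP Section 5 records one change for this endpoint, its place in the test order. It records no change to its imputation rule.

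**The concern.** A treatment-policy estimand uses what was observed after treatment stopped. Assigning flare to everyone who stops for an AE or lack of efficacy is a composite strategy, and neither document declares one for flare. Protocol 7.1 asks subjects who stop study drug to stay in the study for efficacy evaluation where possible, so observed flare-free counts after stopping can exist and would be overwritten.

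The missing time limit adds a second problem. In the terminated study treatment continues to Week 32 (SAP Section 2), and placebo subjects take izokibep from Week 16 (SAP 4.1). Read literally, a placebo-arm subject who stops izokibep for an AE at Week 20 becomes a placebo flare through Week 12. The final flare result could then differ from the Week 12 analysis that SAP 8.6 describes as already done.

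Little in the planned output would reveal this. The tabulation of imputed subjects (9.5, carried over to flare) shows how many received NRI and why, but not how many of them had observed flare-free counts. SAP 9.6.1.1 plans no sensitivity analysis.

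**Working it through.** **1. The rules side by side**

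| Rule for stopping due to AE or lack of efficacy | Missing data required? | Time limit? |
|---|---|---|
| Protocol 9.3.2; SAP 6.7.1.4 (primary estimand) | Yes | None stated |
| SAP 9.5 (primary analysis) | Yes, at Week 12 | Last dose before day 84 |
| SAP 9.6.3, 9.6.4 | Yes, at Week 12 | None stated separately |
| SAP 9.6.1 (flare) | **No** | **None** |

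The conflict with the flare estimand rests on the missing-data column. The day-84 limit is an operational criterion of Section 9.5; it matters because the estimand refers to the primary endpoint's handling and because the endpoint runs only through Week 12.

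**2. Design figure.** The only power figure concerns HiSCR75: 15% against 35%, 125 per arm, two-sided 0.05, unstratified. A pooled normal approximation gives 95.9%, consistent with the stated 95%. No flare rate, flare power or rate of discontinuation for AE or lack of efficacy is given, so the flare rates below are assumptions.

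**3. Effect per recoded subject.** With n = 125 per arm, one fully observed flare-free subject recoded as a flare adds 1/125 = 0.8 points to its arm. If a izokibep and b placebo subjects are recoded, izokibep minus placebo shifts by 0.8 × (a − b) points: in either direction, and zero if a = b.

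**4. Scale against sampling error.** For a common flare rate p, SE = √(2p(1−p)/125).

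| Assumed p | SE (points) | z shift per net subject (0.8/SE) | Net subjects for 1 SE (SE/0.8) |
|---|---|---|---|
| 10% | 3.79 | 0.211 | 4.7 |
| 20% | 5.06 | 0.158 | 6.3 |
| 30% | 5.80 | 0.138 | 7.2 |
| 40% | 6.20 | 0.129 | 7.7 |
| 50% | 6.32 | 0.126 | 7.9 |

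**5. Illustration of direction.** Let f be the flare rate under the estimand and d the share of flare-free subjects caught by the literal rule. The reported rate becomes f + d(1−f). Assume f = 30% on placebo and 15% on izokibep: difference −15.0 points, power 81% at α = 0.0499.

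| Assumed d, placebo / izokibep | Reported rates, placebo / izokibep | Difference (points) | Power |
|---|---|---|---|
| 5% / 5% | 33.5% / 19.3% | −14.2 | 73% |
| 2% / 8% | 31.4% / 21.8% | −9.6 | 40% |
| 8% / 2% | 35.6% / 16.7% | −18.9 | 93% |

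**6. Extra exposure counted.** From Week 12 to Week 32 is 32 − 12 = 20 weeks. In the placebo arm, 32 − 16 = 16 of these are on izokibep.

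**The case against.** The best defence is that this is a dropped qualifier, not a chosen strategy. The section heading, the hypothesis and Table 4 all confine the endpoint to Week 12. The time limit in the antibiotic clause may have been meant for both clauses. Table 5 points to the primary endpoint's handling, and 9.6.1 itself goes on to decide flare from observed or imputed counts. A programmer might therefore apply the intended rule anyway.

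This makes the post-Week-12 reach a risk of literal reading rather than a likely intention. It does not supply the missing-data condition. The term NRI cannot supply it either, since the same sentence applies NRI to antibiotic users whatever their data, and 9.6.3 and 9.6.4 state the condition where it is meant. Extending the time limit to both clauses would still overwrite observed counts before Week 12.

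It can also be said that little hangs on it. Protocol 7.1 expects permanent discontinuation to be uncommon, and flare is tested only after seven other tests succeed. SAP 8.7 treats the inferential results as settled at the primary analysis. The shortened endpoint list in SAP Section 5 names flares through Weeks 4, 16 and 52, not Week 12. The modest consequence stands. But that list omits Week 12 HiSCR75 too, while SAP 8.6, 9.5 and 9.6.1 still specify both analyses in the document that defines the final analysis.

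A last point is that importing the Section 9.5 criteria does more than restore the missing word. That is correct, and the subjects who move should be named.

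**Conclusion.** The concern holds. As written, the discontinuation clause of 9.6.1 contradicts the flare estimand in both documents and departs from every parallel rule. Confidence in the textual mismatch is high.

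The size and direction of its effect are unknown. Each net recoded subject moves the difference by 0.8 points, or the test statistic by 0.13 to 0.21 over assumed flare rates of 10% to 50%. These figures rest on 125 subjects per arm and an unstratified standard error. The clause should be corrected, but it affects only the flare result and no other test in the hierarchy.

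**What to change.** Amend SAP 9.6.1 so that NRI for discontinuation due to AE or lack of efficacy applies only when the Week 12 AN count is missing because of that discontinuation, identified by the Section 9.5 criteria. Otherwise use observed counts, with multiple imputation (MI) for other missing visits.

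State who else moves. Take subjects with no observed flare and an assumed imputed flare probability q of 10% to 50%; each changes its arm's rate by 0.8 × (1 − q), that is 0.72 to 0.40 points:

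- Week 12 count missing, last dose on or after day 84: NRI to MI, lowering the rate.
- Week 12 count missing, stopped for death or disease progression with last dose before day 84: MI to NRI, raising the rate.
- Stopped for AE or lack of efficacy, Week 12 observed but an earlier count missing: NRI to MI, lowering the rate.

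Also state which rule the Week 12 primary analysis used, and document any difference in SAP Section 5 and the CSR, as Protocol 9.3.1 requires for deviations made after unblinding. If a composite strategy was intended, declare it in Table 5 and Section 5 instead.

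The cost is one sentence, one condition in the derivation program and a short note in SAP Section 5 and the CSR.
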